## 8.4.1 Time Period and Frequency for Collecting AE and SAE Information

AEs and SAEs will be collected from time of first dose of study medication through the follow-up contact.

All SAEs will be recorded and reported to the Sponsor or designee within 24 hours, as indicated in Appendix 3. The Investigator will submit any updated SAE data to the Sponsor designee within 24 hours of it being available.

Investigators are not obligated to actively seek AE or SAE after conclusion of the study participation. However, if the Investigator learns of any SAE, including a death, at any time after a subject has been discharged from the study, and he/she considers the event to be reasonably related to the study medication or study participation, the Investigator must promptly notify the Sponsor.

The method of recording, evaluating, and assessing causality of AEs and SAEs and the procedures for completing and transmitting SAE reports are provided in Appendix 3.

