## **1.3** Schedule of Activities

### Table 1: Schedule of Assessments and Procedures

	Study Start	Treatment Period		rt Treatment Period Study		Study End	Early Wit Termin	hdrawal / nation ¥
	Screening	Day 1 (≤7 days)	Week 6 (42 ± 3 days)	Week 12 (42 ± 3 days)	7 ± 3 days after Visit 4	As Soon as Possible after EW/T	7 ± 3 days after EW/T Visit	
	Visit 1	Visit 2	Visit 3	Visit 4 (EOT)	Follow-up	EW/T Visit	Follow-Up	
Informed consent A	X							
Inclusion/exclusion criteria (eligibility review)	X	Review, Update						
Demographics (date of birth, age, gender, race, ethnicity)	X							
CAT ™ training	X							
CAT TMB	X*		X*	X*				
mMRC (administered by study team)	X							
Medical, surgical, smoking history	X	Review, Update						
Prior and concomitant medication	X							
Vital signs (blood pressure and pulse rate)		Х	Х	X		Х		
Height and Weight; BMI calculated		Х						
Brief physical exam C		Х						
Urine pregnancy test D		Х	X	X				
Pre- and post-bronchodilator Spirometry E		Х						
Nebulizer equipment materials dispensing, review, and training; collection at end F		Х	X	Х		X		
Study medication dispensing G		Х	X					
In clinic study medication dosing		Х						
Concomitant medication review		Х	X	X	X	X	Х	
Study medication compliance			X	X		X		
AE and SAE recording		Х	X	X	Х	X	X	
Phone call to subject					Х		Х	

**Note**: Information and details on most of the Study Assessments and Procedures can be found in Section 8.0. \*The CATTM is completed by the subject on paper first before any procedures and assessments. ¥The early withdrawal / termination visit should be conducted as soon as possible. If possible, subjects should remain on study medication through the early termination visit (Section 7.2).

- A. Informed consent must be obtained by the process described in Appendix 2. Consent must be obtained prior to any study procedures being performed.
- B. Following informed consent, the CATTM is performed first before any procedures and assessments.
- C. Assessments of the Cardiovascular, Respiratory, Gastrointestinal, and Neurological systems.
- D. Pregnancy Testing: Pregnancy testing will be conducted on women of childbearing potential only (refer to Appendix 4).

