## 5.1 Inclusion Criteria

- 1. Capable of giving informed consent indicating that they understand the purpose of the study and study procedures and agree to comply with the requirements and restrictions listed in the ICF and in this protocol.
- 2. Aged 40 to 80 years of age inclusive, at the time of screening.
- 3. Sex:
  - Males are eligible to participate if they agree to use contraception as described in the contraceptive guidance (Appendix 4) from screening and throughout the study and for at least 30 days after the last dose of study medication.
  - Females are eligible to participate if they are not pregnant, not breastfeeding, and  $\geq 1$  of the following conditions apply:
    - a) Not a woman of childbearing potential (WOCBP) as defined in Appendix 4.
      - OR
    - b) A WOCBP who agrees to follow the contraceptive guidance in Appendix 4 from screening and throughout the study and for at least 30 days after the last dose of study medication.
- 4. Current or former cigarette smoker with a history of cigarette smoking ≥ 10 pack years. Note: Pipe and/or cigar use cannot be used to calculate pack-year history. Former smokers are defined as those who have stopped smoking at least 6 months prior to screening. Smoking cessation programs are permitted during the study.
- An established clinical history of COPD as defined by the American Thoracic Society (ATS)/European Respiratory Society (ERS) guidelines with symptoms compatible with COPD.
- 6. Pre- and post-bronchodilator (4 puffs of albuterol) spirometry at Visit 2 demonstrating the following:
  - Pre- and post-albuterol  $FEV_1$ /forced vital capacity (FVC) ratio of < 0.70.
  - Post-albuterol  $FEV_1 \ge 30$  % and  $\le 75$ % of predicted normal.
- 7. A score of  $\geq 2$  on the modified Medical Research Council Dyspnea Scale at Visit 1.
- 8. A score of  $\geq 10$  on the COPD Assessment TestTM at Visit 1.
- 9. Demonstrates stable use of dual (LAMA+LABA) or triple (LAMA+LABA+ICS) maintenance therapy, in any form (except nebulized) for at least 8 weeks prior to screening and agrees to continue use for the duration of the study. *Note: The*

number taking LAMA+LABA+ICS will be capped at ten (10). The use of LAMA or LABA alone or with ICS is not permitted (e.g., LABA+ICS, LAMA).

- 10. Capable of withholding short-acting rescue medications for 4 hours, Twice-Daily maintenance therapy for 24 hours or Once-Daily maintenance therapy for 48 hours prior to Visit 2.

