## 5.4 Screen Failures

Screen failures are defined as subjects who consent to participate in the clinical study but did not receive study medication. See Section 7.1.1 for instructions on managing subjects who did not meet the eligibility criteria but received study medication in error.

A minimal set of screen failure information is required to ensure transparent reporting of screen failure subjects to meet the Consolidated Standards of Reporting Trials publishing requirements and to respond to queries from regulatory authorities. Minimal information includes demography, screen failure details, eligibility criteria, and any SAEs.

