#### 6.7.1 **Permitted Medications/Therapy**

Permitted COPD rescue and maintenance medications are provided in Table 4. Subjects must demonstrate stable use of prescribed long-acting maintenance medications for at least 8 weeks prior to screening.

Subjects may continue use of their prescribed inhaled short-acting muscarinic antagonists (SAMA), short-acting  $\beta$ 2 agonist (SABA), LABA+LAMA or LABA+LAMA+ICS in any form (except nebulized) while participating. Changes in any of these treatments should not occur during participation, except in the case of a safety issue. New medications or treatments should not be started during participation unless necessary for safety reasons.

Medication	Condition	
SABA and/or SAMA	For use as rescue medication only during the study, on an as needed	
(e.g., albuterol,	basis.	
ipratropium)	Must withhold prior to Visit 2 spirometry: 4 hours.	
LAMA+LABA $\pm$ ICS	Subjects will be required to remain on their maintenance COPD	
	treatment inhaler(s) at a stable dose for the duration of the study.	
	Must withhold prior to Visit 2 spirometry: 48 (once-daily) or 24	
	(twice-daily) hours.	
	Only approved COPD doses of ICS are permitted for enrollment and	
	during study participation (e.g., Trelegy containing 100 mcg FF).	
	Maintenance therapy should resume once Visit 2 has been completed.	
Abbreviations: COPD = chronic obstructive pulmonary disease; ICS = inhaled corticosteroids;		
LAMA = long-acting muscarinic antagonist; LABA = long-acting $\beta$ 2 agonist; SAMA = short-		
$\mu$ acting muscarinic antagonists: SABA = short-acting B2 agonist		

 Table 4: Permitted Rescue and Background Medications

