## 8.4 Adverse Events

The definitions of an AE or SAE can be found in Appendix 3.

AEs will be reported by the subject.

The Investigator and any designees are responsible for detecting, documenting, and recording events that meet the definition of an AE or SAE and remain responsible for following up AEs that are serious, considered related to the study medication or study procedures, or that caused the subject to discontinue the study (Appendix 3).

As stated in Section 8.1.1.5, medical and COPD condition(s) identified during screening will be documented as medical history and not as an AE unless the condition worsens during the study and meets the definition of an AE.

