### 8.4.7.1 Adverse Events and SAEs

An adverse event (AE) is any untoward medical occurrence in a subject or subject, temporally associated with the use of study medication, whether considered related to the study medication or not. AEs will be collected from time of first dose to follow-up contact. Medical and COPD condition(s) identified during screening will be documented as medical history and not as an AE unless the condition worsens during the study and meets the definition of an AE. Treatment-emergent adverse events (TEAE) are any events that occur after the first dose of study treatment. Serious adverse events (SAE) include any occurrence defined as an AE that results in any of the following:

- Death
- Is life-threatening
- Requires in-patient hospitalization or prolongation of hospitalization
- Results in persistent disability/incapacity
- Is a congenital anomaly/birth defect
- Other

AEs requiring hospitalization include any events at a hospital or emergency ward for observation and/or treatment that would not have been appropriate in the physician's office or outpatient setting. Complications that occur during hospitalization are AEs. Hospitalization for elective treatment of a pre-existing condition that did not worsen from baseline is not considered an AE. For the "Other" criteria for SAEs, medical or scientific judgment should be exercised in deciding whether SAE reporting is appropriate in other situations such as important medical events that may not be immediately life-threatening or result in death or hospitalization but may jeopardize the subject or may require medical or surgical intervention to prevent one of the other outcomes listed in the above definition. These events should usually be considered serious.

Statistical Analysis Plan	Client/Project	Verona Pharma/RPL554-CO-303
	Version and Date	V02 12/11/2024

In addition to seriousness, AEs will be classified based on intensity (mild, moderate, severe), and relatedness/causality (reasonable possibility or no reasonable possibility). AEs will be coded using the Medical Dictionary for Regulatory Activities (MedDRA) and summarized by system organ class (SOC) and preferred term (PT). TEAEs, for the Safety Analysis Set, will be listed and summarized descriptively as the count and percentage of subjects experiencing the event in tabular form. Seriousness, relatedness, and outcome will be identified in the listings. AE summaries will include the following:

- Overall TEAE Summary

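### SAE collection starts at the first dose, yet SAEs must be recorded for screen failures who are never dosed, so serious events between consent and first dose have conflicting rules

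*Protocol*

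**What the plan says.** **Collection window.** Protocol Section 8.4.1 says "AEs and SAEs will be collected from time of first dose of study medication through the follow-up contact". SAP Section 8.4.7.1 repeats it for adverse events: "AEs will be collected from time of first dose to follow-up contact". In Table 1 the row "AE and SAE recording" is marked from Visit 2 onward and is blank at Visit 1.

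**Screen failures.** Protocol Section 5.4: "Screen failures are defined as subjects who consent to participate in the clinical study but did not receive study medication". The same section sets what must be kept for them: "Minimal information includes demography, screen failure details, eligibility criteria, and any SAEs".

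**Definitions.** Appendix 3 defines an adverse event by its link in time to use of study medication. It adds that an event falling outside that definition cannot be an SAE, whatever its consequences.

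**Procedures before the first dose.** Inclusion criterion 10 requires subjects to be able to withhold short-acting rescue medication for 4 hours and "Twice-Daily maintenance therapy for 24 hours or Once-Daily maintenance therapy for 48 hours" before Visit 2. Spirometry before and after albuterol is then done at Visit 2. Table 4 in Section 6.7.1 gives the end of the hold: "Maintenance therapy should resume once Visit 2 has been completed".

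**Follow-up duty.** Section 8.4 makes the investigator responsible for following events that are serious, that led to discontinuation, or that are "considered related to the study medication or study procedures".

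**The concern.** A screen failure has no first dose, so the Section 8.4.1 window never opens for that person, while Section 5.4 asks for that person's SAEs. The days before the first dose are also when the protocol asks subjects to do something they would not otherwise do: stop maintenance inhalers for a day or two and perform spirometry off treatment. If a serious event occurred then, the site would not know from the protocol whether it is an SAE, whether the 24-hour clock applies, or where it would be reported.

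At stake is a complete and timely safety record for consented subjects, and the sponsor's ability to describe the risk of its own screening procedures. Estimation of the responder proportion and of CAT change is not at stake.

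**Working it through.** The plan gives no figure to reproduce here, so the check sets the passages against one another.

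1. **Timeline.** Consent and screening are at Visit 1. Table 1 heads the Visit 2 column with a limit of 7 days. I read this as the Visit 1 to Visit 2 interval, and the stated total participation agrees: 1 week of screening + 12 weeks of treatment + 1 week to the follow-up call = 14 weeks, the figure in the synopsis and in Section 4.3.

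2. **Order within Visit 2.** Inclusion criterion 6 depends on the Visit 2 spirometry, and Section 6.3.1 places dosing after eligibility is confirmed. Spirometry and the albuterol given for it therefore precede the first dose.

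3. **Position of the withholding period.** It starts 24 or 48 hours before Visit 2 and ends once Visit 2 is complete. The first dose is given during Visit 2, so most of the hold falls before the collection window and its last part falls inside it.

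4. **Screen failures.** Section 5.4 names SAEs as a required data item. Section 8.4.1, Table 1 and Appendix 3 supply no window, visit or definition under which a never-dosed subject can have one. Read literally, the Appendix 3 definition leaves the Section 5.4 item empty.

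5. **Subjects dosed later.** Sections 8.1.1.5 and 8.4 send conditions identified during screening to medical history, unless they worsen during the study and meet the adverse event definition. Section 8.1.2 has history changes recorded at Visit 2 before dispensing. None of these passages asks for seriousness, causality or a 24-hour report.

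6. **SAP outputs.** The serious-event tables and listing (Section 10) are restricted to treatment-emergent events in the Safety Analysis Set. Medical history is summarised and listed for that set only (Section 8.4.2). The screen-failure listing, 16.1.2, covers all subjects, but its title names only the failure and its reason. The shells are in a separate document, so its columns cannot be checked. No listed output is assigned to a pre-dose SAE.

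7. **Amount of time involved.** With about 20 dosed subjects and at most 7 days each, 20 × 7 = 140 subject-days, or 140 / 365.25 ≈ 0.38 subject-years. At most 20 × 2 = 40 of those subject-days fall in the withholding period, if every subject is on once-daily therapy. Each screen failure adds up to 7 days; their number is not given.

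**The case against.** A fair defence is that the protocol does not leave these events unrecorded.

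- Section 5.4 itself calls for SAEs in screen failures. The serious event that withholding would most plausibly provoke, a hospitalisation for COPD, meets exclusion criterion 1, so the subject becomes a screen failure and Section 5.4 applies.
- Events in subjects dosed later can reach medical history.
- Section 8.4.1 also requires prompt notice of an SAE learned of after discharge if it is thought related to study participation.
- Appendix 2 has the investigator notify the ethics committee of SAEs or other significant safety findings as that committee's procedures require.
- Section 8.4.1 says when routine collection runs and does not forbid recording an earlier event. Starting at first dose is also coherent with an adverse event definition based on use of the drug.
- The Section 8.4 follow-up duty concerns events that already qualify as adverse events, so it does not by itself create a duty to collect before dosing.

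Most of this stands, and it rules out three stronger readings that a reader might infer. The documents do not support saying that pre-dose serious events are never captured, because of Section 5.4 and the history record. They do not support saying that the withholding period lies wholly outside the window, because it continues past the first dose. Nor do they show that a site could not satisfy both sections in practice.

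The defence does not remove the conflict itself. Section 5.4 names a data item that Appendix 3 defines out of existence before dosing. Medical history does not replace SAE assessment and reporting, and the post-discharge rule has no counterpart for a subject still in screening.

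**Conclusion.** The point holds as an inconsistency in the safety-reporting rules. For serious events between consent and first dose, the collection rules conflict for screen failures. For subjects dosed later, such events are left to medical history, without SAE assessment, 24-hour reporting or a serious-event output.

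The period is at most 7 days per consented subject, about 0.38 subject-years over 20 dosed subjects plus the screening time of the failures, so few events are expected. This rests on reading the Visit 2 heading as the screening interval. The documents give neither a screen-failure count nor an event rate, so I put no number on expected SAEs.

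The change is worth making because it alters what the site records and reports while subjects are off maintenance therapy at the protocol's request. It does not bear on the primary result, the CAT analyses or the treatment-emergent summaries.

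**What to change.** 1. Amend Protocol Section 8.4.1 so that SAEs, at minimum those related to study procedures, are collected and reported within 24 hours from signature of informed consent. Other adverse events continue from first dose.
2. Mark SAE recording at Visit 1 in Table 1, in both the protocol and the SAP copy.
3. Extend the Appendix 3 adverse event and SAE definitions to cover pre-dose SAEs. Without this, the first change has no effect, because a pre-dose event would still fail the definition.
4. Amend the collection sentence in SAP Section 8.4.7.1 to match, and leave the treatment-emergent definition as it is.
5. Add one SAP listing of pre-dose SAEs for all consented subjects, including screen failures, kept apart from the treatment-emergent outputs.

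The cost is protocol and SAP wording, one schedule cell, one listing and a few extra SAE forms at most. No efficacy or treatment-emergent analysis changes. If screening has already closed, the listing can only be filled from the screening log and source records, and the report should say so.

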## 8.4.2 Method of Detecting AEs and SAEs

Care will be taken not to introduce bias when detecting AEs and/or SAEs. Open-ended and non-leading verbal questioning of the subject is the preferred method to inquire about AE occurrences.

## 8.4.3 **Regulatory Reporting Requirements for SAEs**

Prompt notification by the Investigator to the Sponsor of an SAE is essential so that legal obligations and ethical responsibilities towards the safety of subjects and the safety of a study medication under clinical investigation are met.

The Sponsor has a legal responsibility to notify both the local regulatory authority and other regulatory agencies about the safety of a study medication under clinical investigation. The Sponsor will comply with country-specific regulatory requirements relating to safety reporting to the regulatory authority, Institutional Review Boards (IRB)/Independent Ethics Committees (IEC), and Investigators.

Investigator safety reports must be prepared for suspected unexpected serious adverse reactions (SUSAR) according to local regulatory requirements and Sponsor policy and forwarded to Investigators, as necessary.

An Investigator who receives an Investigator safety report describing an SAE or other specific safety information (e.g., summary or listing of SAEs) from the Sponsor will review and then file it along with the IB and will notify the IRB/IEC, if appropriate according to local requirements.

## 8.4.4 Follow-up of AEs and SAEs

After the initial AE/SAE report, the Investigator is required to proactively follow each subject at subsequent visits/contacts. All SAEs will be followed until resolution, stabilization, the event is otherwise explained, through the follow-up contact, or the subject is lost to follow-up (as defined in Section 7.3). Further information on follow-up of AEs and SAEs is given in Appendix 3.

## 8.4.5 Pregnancy

Details of all pregnancies in female subjects will be collected after the start of study medication and until 30 days after the last dose of study medication.

If a pregnancy is reported, the Investigator should inform the Sponsor within 24 hours of learning of the pregnancy and should follow the procedures outlined in Appendix 4.

Abnormal pregnancy outcomes (e.g., spontaneous abortion, fetal death, stillbirth, congenital anomalies, ectopic pregnancy) are considered SAEs.

## 8.4.6 Adverse Events of Special Interest

Adverse events of special interest have not been identified for ensifentrine.

# 8.4.7 Disease-related Events and/or Disease-related Outcomes Not Qualifying as AEs or SAEs

Disease-related events and/or disease-related outcomes should generally not be recorded or reported as an adverse event.

COPD exacerbations are an expected disease-related outcome, unless the exacerbations manifest in an unusual or uncharacteristic manner. COPD exacerbations including daily expected COPD symptoms (e.g., dyspnea, chest tightness, wheezing, cough, sputum, that are not associated with the dosing event) will not be collected as an AE unless they meet the definition of an SAE.

## 8.4.8 Device Incidents

The Investigator, or responsible person according to local requirements (e.g., the head of the medical institution), will comply with the applicable local regulatory requirements relating to the reporting of device incidents to the IRB/IEC, device manufacturer, or regulatory authorities, as required.

A device incident is defined as an incident related to the failure of a medical device, deterioration in its effectiveness, or inadequacy in its labeling or directions that led to the death or serious deterioration in health of a subject, user, or other person, or could do so were it to recur.

## 8.5 Treatment of Overdose

An overdose is defined as a dose greater than the total daily doses prescribed in this study which results in clinical signs and symptoms. These should be recorded by the investigator on the AE/SAE pages.

In the event of an overdose the investigator should use clinical judgement in treating the overdose and contact the study Medical Monitor. Verona Pharma is not recommending specific treatment guidance for overdose and toxicity management.

